10. ASSESSMENT OF SAFETY

Respective safety measures comprise inclusion/exclusion criteria for participation in clinical studies with M7824, guidance for prevention, monitoring, and medical management of potential risks, as well as guidance on study treatment interruption or discontinuation.

10.1 General Assessments

The safety profile of M7824 will be assessed through the recording, reporting, and analysis of baseline medical conditions, AEs, physical examination findings, including vital signs, laboratory tests, ECOG PS, and 12-lead electrocardiogram (ECG) recordings.

The AE reporting period for safety surveillance begins when the participant receives the first dose of the investigational agent and continues until last Safety Follow-up visit or before start of any anticancer therapy, whatever comes first.

The safety assessments will be performed according to the Schedule of Assessments in Table 1.

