8.2 Withdrawal from Study

1. A participant may withdraw from the study at any time, at his/her own request (i.e., withdrawal of consent), and without giving a reason.
2. The participant may be withdrawn by the Investigator due to participation in another clinical study.
3. The participant may be withdrawn at any time at the discretion of the Investigator for safety, behavioral, compliance, or administrative reasons.
4. The Schedule of Assessments specifies the data to be collected at study discontinuation and follow up, and any additional evaluations that need to be completed.

In case of withdrawal from the study:

1. The appropriate electronic case report forms (eCRFs) for the End-of-Treatment visit must be completed.
2. The day of withdrawal will correspond to the day of end of treatment and the assessments scheduled for the visit should be performed, if possible, with a focus on the most relevant assessments.
3. Participants will be asked to continue safety and survival follow up, which includes the collection of data on survival, patient reported outcome (PRO) questionnaires, and subsequent anticancer therapy. After completion of the Follow-up period or after the End of Treatment visit, whatever is applicable, the appropriate eCRF section for Study Termination must be completed.

If the participant is enrolled into a new study or any new therapy post-withdrawal from the study, the Safety Follow-up visit should be scheduled prior to the start of the new treatment irrespective of the 28-day safety follow up period.

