12. ADVERSE EVENTS

The investigator is required to report to the supporting company EMD Serono or its representative all AEs occurring during the clinical study (Title 21 Code of Federal Regulations [CFR] Part 312.64[b] and International Conference on Harmonization [ICH] E6 [R2]).

At each study visit, subjects will be evaluated for new Adverse Events (AE) and the status of existing AEs. All AEs observed from the date of the first administration of study treatment until the end of the follow-up period of the study (study cut-off date) are to be recorded on the AE page of the e-CRF. The date of onset and resolution, determination of seriousness, severity, grade, corrective treatment, outcome, and relationship to study treatment (M7824, Radiotherapy) will be recorded for all AEs.

All Serious Adverse Events (SAEs) occurring from the date of onset of the study treatment until the end of follow-up period of the study (study cut-off date) will be collected.

This study will utilize the NCI Common Terminology Criteria for Adverse Events (CTCAE) version 5.0 for adverse event (AE) reporting. The CTCAE version 5.0 is located on the CTEP website at http://ctep.cancer.gov/protocolDevelopment/electronic_applications/ctc.htm.

An Adverse Event is defined as any untoward medical occurrence in a patient regardless of its causal relationship to study treatment. An AE can be any unfavorable and unintended sign (including any clinically significant abnormal laboratory test result), symptom, or disease temporally associated with the use of the study treatment, whether or not it is considered to be study drug(s) related. Included in

this definition are any newly occurring events and any previous condition that has increased in severity or frequency since the administration of study therapy.

The investigator (or physician designee) is responsible for verifying and providing source documentation for all adverse events and assigning the attribution for all adverse events for subjects enrolled.

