Serious Adverse Events (SAEs) will be reported within 24 hours of acknowledge by the study team, unless it occurs over the weekend or holidays, when it will be notified in the first business day. They are defined as any adverse drug event (experience) occurring at any dose that results in any of the following outcomes: death; a life-threatening adverse drug experience; inpatient hospitalization or prolongation of existing hospitalization; a persistent or significant disability/incapacity; a congenital anomaly/birth defect. Important medical events that may not result in death, be life threatening, or require hospitalization may be considered an SAE, when, based upon medical judgment, they may jeopardize the patient and may require medical or surgical intervention to prevent one of the outcomes listed in the definition.

Toxicities will be assessed by the treating physician/s according to the CT Cv5 criteria.

Early onset (acute) toxicities occurring prior to 90 days will also be considered late onset (chronic) toxicities if they persist for at least one day beyond the 90 days used to define late onset (chronic) toxicities. In analyses that examine acute and chronic toxicities separately, those toxicities that began as acute but became chronic will be included in both the analysis of acute toxicities and in the analysis of chronic toxicities.

Immune-related AEs should be documented as an 'Adverse Event of Special Interest (AESI)', and it is recommended to involve the Medical Monitor at first incidence and subsequently as needed for follow up. Details of the diagnostic work up will be requested by the study team. Immune-related AEs are described in Section 0.

For reporting irAE severity/toxicity grading, refer to NCI-CTCAE v.5 toxicity grading system.

Toxicities related to radiation therapy include: Pain, mucositis, constipation, dysphagia, odynophagia, hemoptysis, epistaxis, trismus, fatigue, weight loss, dysgeusia, nausea, radiation dermatitis, myelosuppression, skin erythema, subcutaneous fibrosis, esophagitis, myelitis, superficial soft tissue fibrosis and esophageal stricture.

Toxicities related to IO therapy are described in detail in the investigator's brochure.

Toxicity monitoring: Both Acute (From radiation start to 90 days after completion of radiation therapy) and Late (90 days to 2 years from the completion of radiation therapy) side effects of radiation therapy will be documented and graded according to the NCI-CTCAE version 5.0.

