- All events occurring during the conduct of a protocol and meeting the definition of a SAE must be reported to the IRB in accordance with the timeframes and procedures outlined in "The University of Texas M. D. Anderson Cancer Center Institutional Review Board Policy for Investigators on Reporting Serious Unanticipated Adverse Events for Drugs and Devices". Unless stated otherwise in the protocol, all SAEs, expected or unexpected, must be reported to the IND Office, regardless of attribution (within 5 working days of knowledge of the event).
- **All life-threatening or fatal events**, that are unexpected, and related to the study drug, must have a written report submitted within **24 hours** (next working day) of knowledge of the event to the Safety Project Manager in the IND Office.
- Unless otherwise noted, the electronic SAE application (eSAE) will be utilized for safety reporting to the IND Office and MDACC IRB.
- Serious adverse events will be captured from the time of the first protocol-specific intervention, until 90 days after the last dose of drug, unless the participant withdraws consent. Serious adverse events must be followed until clinical recovery is complete and laboratory tests have returned to baseline, progression of the event has stabilized, or there has been acceptable resolution of the event.
- Additionally, any serious adverse events that occur after the 90 day time period that are related to the study treatment must be reported to the IND Office. This may include the development of a secondary malignancy.

Reporting to FDA:

- Serious adverse events will be forwarded to FDA by the IND Sponsor (Safety Project Manager IND Office) according to 21 CFR 312.32.

It is the responsibility of the PI and the research team to ensure serious adverse events are reported according to the Code of Federal Regulations, Good Clinical Practices, the protocol guidelines, the sponsor's guidelines, and Institutional Review Board policy.

SAEs, whether related or not related to study drug, must be reported to EMD Serono within 24 hours. SAEs must be recorded on BMS approved form.

If only limited information is initially available, follow-up reports are required. (Note: Follow-up SAE reports should include the same investigator term(s) initially reported.)

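### The plan gives conflicting end dates for adverse-event collection and for the study, and conflicting EQ-5D schedules; following section 10.1 and Table 1 would leave late toxicity under-recorded and a 21-month gap in EQ-5D

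*Combined protocol and SAP*

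**What the plan says.** **AE collection.** Section 10.1 starts AE reporting at the first dose, says that it "continues until last Safety Follow-up visit or before start of any anticancer therapy, whatever comes first", and refers to Table 1 for the schedule. The visit is not defined. The AE row of Table 1 is marked at screening, on treatment and at the First Follow-up (90 days after the last dose, +/-14 days). It is empty in the six-monthly year 2-5 column. Section 12 is broader: "At each study visit, subjects will be evaluated for new Adverse Events (AE) and the status of existing AEs". It says that all AEs from first treatment "until the end of the follow-up period of the study (study cut-off date) are to be recorded on the AE page", and that "Late (90 days to 2 years from the completion of radiation therapy) side effects of radiation therapy will be documented and graded".

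**Serious events.** Section 12 first says that all SAEs "until the end of follow-up period of the study (study cut-off date) will be collected". Under SAE reporting it says "Serious adverse events will be captured from the time of the first protocol-specific intervention, until 90 days after the last dose of drug", after which "any serious adverse events that occur after the 90 day time period that are related to the study treatment must be reported". Section 8.2, on withdrawn patients, schedules a safety visit "irrespective of the 28-day safety follow up period". That period appears nowhere else.

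**Study end.** Section 8.4 sets it at 1 year after the last participant's last dose. Section 13.5 gives a total of 29 months. Table 1 has visits in years 2 to 5.

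**EQ-5D.** Table 1 has screening, 3 and 24 months. Section 5.1 puts a questionnaire battery that includes EQ-5D at completion of reirradiation and at follow-up visits to 24 months, and refers to Table 2 for this. Table 2 is the infusion-reaction table. Section 13.6 has patient-reported outcomes about every 3 months to 24 months.

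**The concern.** Two secondary objectives in section 1.3 rest on these schedules: acute and late CTCAE toxicity, and the QALY comparison with historic SBRT reirradiation. Both need data that must be collected prospectively.

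A site working from 10.1 and the visit table would stop recording non-serious events well before 2 years after SBRT. The resulting error has one direction, since late toxicity would look lower than it is. It would also be informative, because patients who start new anticancer therapy leave AE collection first. No formal test of late toxicity is planned, but the rate would naturally be read beside the late grade 3 rates of 10% to 30% that section 2.3 cites for SBRT.

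The study-end conflict makes this worse. Section 12 relies on a study cut-off that has no single date, so even the broader rule does not fix how long late effects are followed. For QALYs, utility between months 3 and 24 would have to be interpolated.

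**Working it through.** **Inputs.** Cycles of 28 days with doses on days 1 and 15 (6.2.2); C1-C12 (Table 1); SBRT starting 2 weeks after the first dose (13.2) and lasting two weeks (6.1.3); late window from 90 days to 2 years after SBRT (12); 21 patients, 2 per month, 11 months of accrual, 1.5 years of further follow-up (13.5). Assumptions: SBRT ends on day 28, 2 years is 730 days, and the 21 are all the patients enrolled.

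**1. The plan's own figure.** 21 / 2 = 10.5, rounded up to 11 months; 11 + 18 = 29 months. This reproduces.

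**2. Late-window coverage under 10.1 and Table 1.** The window runs from day 28 + 90 = 118 to day 28 + 730 = 758, which is 640 days. The last scheduled dose (C12D15) is on day 11 x 28 + 15 = 323. Coverage = (AE end - 118) / 640.

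| Case | AE end (day) | Coverage |
|---|---|---|
| Full course, 90-day visit | 323 + 90 = 413 | 295/640 = 46% |
| Same, visit 14 days early | 399 | 281/640 = 44% |
| Same, visit 14 days late | 427 | 309/640 = 48% |
| Full course, 28-day reading of 8.2 | 351 | 233/640 = 36% |
| Last dose at C3D15 (day 71), 90-day visit | 161 | 43/640 = 7% |
| New therapy at month 6 (day 183) | 183 at the latest | at most 65/640 = 10% |

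The last two rows are examples, not forecasts. Moving the end of SBRT to day 23 or day 29 changes the first row only to (413 - 113)/640 = 47% or (413 - 119)/640 = 46%.

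**3. Study end.** Take 21 starts half a month apart, from month 0 to 10 or from 0.5 to 10.5. SBRT ends 28 days, or 0.92 months, after the start. C12D15 falls 322 days, or 10.58 months, after the start.

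- Section 8.4, last dose at C12D15: last start + 10.58 + 12 = month 32.6 to 33.1 (33.6 if the last start is month 11).
- Section 8.4, last dose at 1 year: last start + 24 = month 34.0 to 34.5 (35 if the last start is month 11).
- Table 1 through year 5: 11 + 60 = month 71.

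A patient has exactly 2 years after SBRT if start + 24.92 is no later than the study end. With the +/-28-day window of the Follow-Up column, start + 24.92 - 0.92 = start + 24 is enough.

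| Study end | Exactly 2 years after SBRT | Within the visit window |
|---|---|---|
| Month 29 (13.5) | 8-9 of 21 | 10-11 of 21 |
| 8.4, last dose at C12D15 | 16 of 21 | 18 of 21 |
| 8.4, last dose at 1 year | 19 of 21 | 21 of 21 |

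Sections 8.4 and 13.5 would coincide only if the last participant's last dose came 29 - 12 - 11 = 6 months after enrolment. No patient reaches month 36 under either end date, since the earliest start (month 0) would need a study end at month 36.

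**4. EQ-5D.** The Table 1 gap is 24 - 3 = 21 months, with 3 forms per patient. Section 13.6 gives 9 (completion of reirradiation plus months 3, 6, ..., 24), or 10 with baseline.

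**The case against.** The strongest reply is that late toxicity has its own rule. Section 10.1 concerns the safety profile of M7824, and its period is for safety surveillance. Section 12 deals specifically with late radiation effects and takes them to 2 years. A specific rule can be read alongside a general one. The last Safety Follow-up visit need not be the 90-day visit; a later visit would leave new therapy as the only early stop in 10.1. The empty Table 1 cell is weak evidence by itself, since the LSIDS-HN row is also empty although the footnote schedules it. This stands, and it makes the truncation conditional. It does not remove the conflict: nothing says that section 12 prevails, and 10.1 sends sites to the table with the narrower schedule.

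It can also be said that the two SAE statements separate collection from reporting to the IND Office, and that 29 months is a projection while 8.4 is the definition. Both readings are possible, and both are settled by stating one date. On EQ-5D, section 2.7 aims to limit survey burden, and the historic control's EQ-5D schedule is not given, so the gain for the comparison cannot be quantified.

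Three stronger readings are tempting but not supported:

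- That late toxicity is lost altogether. Section 12 covers it if followed. Otherwise related SAEs after 90 days are still reported, and HN-LEF, CROM and swallow studies continue at 18-24 months (not for anterior skull base patients).
- That the reported late rate falls in proportion to coverage. Section 12 also counts acute toxicities that persist past day 90 as late, related late SAEs remain, and the cited 10-30% has no stated time horizon.
- That the 13.2 wording, 12 cycles every 2 weeks, means a course of about half a year. The same sentence says up to 1 year, and Table 1 lists C1-C12 with days 1 and 15 in 28-day cycles. I calculated on that basis; the wording still has to be reconciled.

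**Conclusion.** The conflicts are in the current text and should be resolved. Their effect on late toxicity depends on which section a site follows. Under section 12 the endpoint is covered. Under 10.1 and Table 1, with the 90-day visit as the safety visit, a fully treated patient is observed for about 46% (44-48%) of the late window, and non-serious late toxicity is under-recorded. Coverage is lower after early discontinuation or new therapy.

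A 29-month close leaves 8-9 of 21 patients with 2 years after SBRT. Under 8.4 with full treatment 16-19 do exactly, and 18-21 within the visit window, so a reader should not conclude that the last patient can never have a 2-year visit. These counts assume even accrual at the planned rate.

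For EQ-5D, a coarse QALY remains possible from Table 1, but values not collected during the 21 months cannot be recovered. Only secondary objectives are at stake; the primary endpoint is not affected.

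**What to change.** One amendment:

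- In Table 1, mark AE evaluation of radiation- and treatment-related events at the existing follow-up visits through 2 years after SBRT, regardless of new anticancer therapy, and align 10.1 with section 12.
- State which Table 1 visit is the Safety Follow-up visit, and give one SAE end date in section 12.
- Add EQ-5D at 6, 12 and 18 months, where MDASI-HN is already collected. Align 5.1 and 13.6 with Table 1, and correct the Table 2 reference.
- Restate the 13.5 duration to agree with 8.4. Alternatively, state a late-toxicity horizon that all patients can reach: if month 29 is kept, the last patient has 29 - 10.5 - 0.92 = 17.6 months after SBRT (18.1 with a last start at month 10, 17.1 at month 11).
- Reconcile the cycle wording of 6.2.2 and 13.2, since the 8.4 end date depends on it.

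The cost is modest. AE review is added at visits that already include a physical examination, with at most 3 x 21 = 63 short EQ-5D forms. Attribution is harder after new therapy, although section 12 already records the relationship to M7824 and to radiotherapy. The secondary report comes later: 4-6 months after month 29 if 8.4 is adopted (33 - 29 to 35 - 29), or 6-7 months if every patient must have exactly 2 years after SBRT (10 + 24.92 = 34.9 to 11 + 24.92 = 35.9). The primary analysis need not move.

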10.2 Adverse Drug Reactions Requiring Treatment Modification

Clinical Laboratory Assessments

It is essential that the Supporting company EMD Serono or designee be provided with a list of laboratory normal ranges before shipment of study drug. Any change in laboratory normal ranges during the study will additionally be forwarded to the CRO and the Supporting company EMD Serono.

All routine laboratory analyses will be performed at a laboratory facility local to the study site, and relevant results must be available and checked before administration of treatment (details to be provided in the Laboratory Manual).

If a participant has a clinically significant abnormal laboratory test value that is not present at baseline, the test should be closely monitored until the test value has returned to the normal range or the Investigator has determined that the abnormality is chronic or stable.

The report of the results must be retained as a part of the participant's medical record or source documents.

Abnormal laboratory findings and other abnormal investigational findings (eg, on an ECG trace) should not be reported as AEs unless they are associated with clinical signs and symptoms, lead to treatment discontinuation, or are considered otherwise medically important by the Investigator. If a laboratory abnormality fulfills these criteria, the identified medical condition (eg, anemia, increased ALT) must be reported as the AE rather than the abnormal value itself.

See the Schedule of Assessments in Table 1 for further details.

Specific Planned Assessments or Adverse Events of Special Interest

AESIs are serious or non-serious AEs specific to known mechanism of action of the treatment drug that are of clinical interest requiring ongoing monitoring and rapid communication for optimal on-time management.

IRRs, including immediate hypersensitivity

Any signs or symptoms experienced by participants during the infusion or any event occurring during or within one day of drug administration should be evaluated as potential IRRs. IRRs are common ADRs with monoclonal antibodies (mAbs) timely related to drug administration and have been reported as anaphylaxis, anaphylactoid reactions and cytokine release syndrome, among other terms used. IRRs are an AESI for M7824, and important identified risks (adverse reactions) for M7824, the precautions and management are discussed in Section 0.

Immune-related adverse events (irAEs)

Immune-related AEs are defined as off target side effects associated with exposure of an immunogenic drug and are consistent with an immune mechanism. In the process of identification of irAEs, any possible etiology of neoplastic, infectious, metabolic, toxin, or any other factor should be ruled out. Serologic, histologic (biopsy), and/or immunologic results should be obtained to evaluate the differential diagnosis and/or support an immune-mediated cause. Immune-related AEs are AESIs for M7824 and important identified risks for M7824, the precautions and management are discussed in Section 0.

Skin adverse events

Skin AEs are AESIs for M7824, and include 2 potential mechanisms:

1. Skin AEs possibly due to TGF- β inhibition: rash with hyperkeratosis, KA, and SCC. Skin lesions with hyperkeratoses, keratoacanthoma, cSCC possibly due to TGF- β inhibition are identified risks for M7824. For more information, see Section 0.

Treatment-related skin lesions with hyperkeratosis, KA, cSCC possibly due to TGF- β inhibition were reclassified as important identified risks (adverse reactions) at the end of the safety reporting period of July 2017; however, they have been manageable and did not lead to permanent discontinuations in Studies EMR200647-001/EMR200647-008.

2. Immune-related skin AEs (irAEs) possibly mediated by PD-L1 inhibition (events in this category are also reported under irAEs). For more information, see Section 0.

Treatment-related anemia adverse events

Anemia is considered a potential risk based on toxicological findings with M7824 in the cynomolgus monkey indicating a decrease in Hgb, red blood cells (RBCs), and hematocrit that was fully reversible or showed a substantial trend toward recovery. Treatment-related anemia AEs are AESIs for M7824. A consistent clinical risk of treatment-related anemia on M7824 was not observed in Study EMR200647-001. As summarized in the Investigator Brochure, treatment-related anemia was reported in 6.1% (n=23)

of the participants from a number of cohorts. For more information, see Section 0 and refer to the Investigator Brochure.

Alterations in wound healing or repair of tissue damage

Due to the involvement of TGF- β in repair of skin and other tissue injuries, alterations in wound healing or repair of tissue damage is considered a potential risk. No AEs have been reported in Phase I studies. For any surgeries conducted post-treatment initiation, surgical wound healing will be closely monitored.

Embryo fetal toxicities

Embryo fetal toxicities are a known risk of the PD-1/PD-L1 targeting class. Animal models link the PD-1/PD-L1 signaling pathway with maintenance of pregnancy through induction of maternal immune tolerance to fetal tissue (Guleria, 2005; Leber 2010; Wafula, 2009; Zenclussen 2013). Embryofetal and reproductive toxicities have also been investigated in animal models for a humanized mAb targeting TGF- β 1. At a dose as high as 30 mg/kg, no maternal reproductive toxicity or embryofetal lethality was observed (Hilbush 2016).

Respective safety measures comprise inclusion/exclusion criteria for participation in clinical studies with M7824, guidance for prevention, monitoring, and medical management of potential risks, as well as guidance on study treatment interruption or discontinuation.

Methods of AESI recording and reporting will follow the guideline for AE recording and reporting. Refer to the Investigator Brochure for reporting the identified risks.

Embryo fetal toxicity is an important potential risk of M7824. An appropriate contraception warning is provided as part of inclusion criteria. Pregnant and breastfeeding women are not allowed in the M7824 study and adequate contraceptive measures are recommended during the study to minimize or eliminate the potential risk to the developing fetus.

Functional and patient reported outcomes include but are not limited to:

- Validated clinical grading criteria (Head and Neck-Lymphedema and Fibrosis, HN-LEF)
- Patient-reported measures of head and neck fibrosis (Lymphedema Symptom Inventory Distress Scale, L-SIDS)³
- Radiographic dysphagia grade (Dynamic Imaging Grade of Swallowing Toxicity, DIGEST)
- Cervical range of motion (CROM).

Biomarker Assessments

Due to limited understanding of the biological activities induced by M7824 and radiation in cancer subjects, biomarker assessment will be conducted to examine if the doses are associated with relevant antitumor immune activities. As part of the translational work, this trial will serve to:

1. Evaluate PD-L1 expression as a predictor of response
2. Evaluate the effect on TGF β concentrations in plasma.
3. Evaluate potential predictive / prognostic biomarker candidates related to the drug and / or the cancer (such immune infiltrating populations, tumor mutational burden, systemic cytokine profiles)
 - a. Pancancer Immune Profiling Formalin-Fixed Paraffin-Embedded (FFPE) based assay using Nanostring or HTG technology.
 - b. Immune infiltrating populations will be analyzed by immunohistochemistry (IHC), and Multiplex IF analyses.
 - i. IHC markers will include, but are not limited to, PD-L1 (clone E1L3N, 405.9A11, 28-8, EPR1161(2), SP142, SP263, 22C3, E1J2J), CD20, CD61, LAG3, PD1, CD21, CD66b, OX40, CD3, CD3, CD68, B7-H3 (CD276), CD4, CD33, CD73, B7-H4 (VTCN1), CD5, CD38, CD137, TIM-3, CD8, CD45 LCA, FOXP3, VISTA, CD11b CD45 RO, Granzyme B, CD14, CD56, ICOS, CD19, CD57 (Leu-7), IDO-1.
 - ii. Multiplex IF Analysis. Up to 10 immune markers, various panels of immune markers may be utilized. Panel #1, CD3, CD8, CD68, PD-L1, PD-1 pan-cytokeratin and DAPI; Panel #2, CD20, CD45RO, FOXP3, Granzyme B, CD57, pan-cytokeratin and DAPI. Myeloid panel 5: Arg1, Cd68, CD11B, CD33, CD14, CD66B, AE1/AE3/, DAPI. For multiplex IF analysis, we will use the Opal chemistry and multispectral microscopy Vectra system (Perkin-Elmer) which includes the Nuance software; analysis will be performed using the InForm software. From various optimized panels, additional will be selected according the results of the gene expression analysis and may include other immunotherapy targets (e.g., OX-40, Vista, GITR, TIM-3, LAG-3, NKP46/CD16, etc.) and proliferation markers (e.g., Ki67).
 - iii. RNAscope. TGF- β and other additional markers may be analyzed by RNA scope.
 - c. Immune infiltrating populations and systemic cytokine profiles

i. Blood collections and biopsies will be collected for immune studies under the supervision of the Translational Molecular Pathology Immunoprofiling Lab (TMP-IL) at MD Anderson.

ii. Fresh tissue will be available for flow cytometry for assessment of the proportion of MDSC, macrophage, DC and NK cell subsets within the Live CD45+ cells in panel 3. The expression of checkpoint ligands will be explored using panel 4. Live cells will be sub-gated as CD45-negative to exclude immune cells. EPCAM will be used as a marker of

tumor cells and CD90 as a fibroblast marker. The expression of CD80, CD86, GITR-L, ICOS-L, MIC A/B, B7-H3, B7-H4, CD73, PD-L2, OX40L and other relevant immune cells will be assessed.

iii. In peripheral blood, evaluation by circulating immune populations will include, but not be limited to, CD4⁺, CD8⁺, NK, T_{reg}, monocytes and neutrophils as outlined by the Schedules of Assessments (**Tables 1**). High order flow cytometry panels will be designed. The panels will focus on 1) delineation of major immune cell types (T cells, B cells, NK cells, DC), 2) determination of T cell differentiation status and limited functionality (IFN γ , TNF α , GB) and 3) defining the expression level of costimulatory and coinhibitory molecules on T cells. The proposed studies will be conducted retrospectively on cryopreserved PBMCs.

v. Serum Cytokine Analyses. Cytokines (IFN- γ , IL-1 α , IL-2, IL-4, IL-5, IL-8, IL-10, IL-12p70, IL-13, and TNF- α) will be measured in the serum using the Meso Scale Discovery Platform (Rockville, MD). This technology allows for the detection of up to 40 analytes per well and uses a very low sample volume. This method has a sensitivity up to 1000 fold higher than traditional ELISA assays with a large linear range of 3-4 logs. The instrument performs immunoassays utilizing electrochemiluminescence to detect the signal in a 96 well plate format. This technology can be utilized for either single agent detection or in multiplex format. A wide menu of validated single or multiplex kits for the detection of 1 to 40 analytes are available from the manufacturer and can be customized.

d. Mutational profiling

- i. Genomic profile will be assessed via next generation sequencing in a panel of 409 genes that sequences known hotspots to a coverage of at least x250 coverage depth performed in the Molecular Diagnostic Laboratory (MDL) at MD Anderson. The lab is CAP accredited and CLIA certified to perform high complexity molecular testing for clinical purposes.
- ii. TGF β signaling pathway mutations may also be assessed via this panel which will include, but not limited to, TGF β R2, ACVR2A, SMAD2 and SMAD4.

iv. iv. Circulating free DNA (cfDNA) will be analyzed in peripheral blood using the Guardant Health platform to monitor tumor response and progression. Identified gene mutations will be correlated with target DNA sequencing in the tumor sample.

i.

b. TCR sequencing

TCR sequencing analysis may be performed using DNA from tumor tissues as well as PBMC. Briefly, 500 ng tumor DNA or 3-6 ug PBMC DNA will be subjected to high throughput TCR V β CDR3 sequencing on an Illumina HiSeq sequencer with at least 5-fold coverage by ImmunoSEQ™ sequencing (Adaptive Biotechnologies, Seattle, WA). TCR diversity and

clonality (defined as $1 - \text{entropy}/\log_2(\#)$ of productive unique sequences, where the entropy term takes into account the varying clone frequency) will be calculated using a software by Adaptive Technologies. T-cell repertoire diversity and clonality will be correlated with clinic-pathological parameters such as response to treatment, survival and immune infiltrating profile as well as genomic profiles (total mutation burden, non-synonymous mutation burden, predicted neoantigen burden, clonal mutation burden and clonal predicted neoantigen burden). TCR profile generated from treatment-refractory tumors at the time of disease progression will be compared to data from pre-treatment tumor samples to explore the TCR repertoire evolution of these tumors under therapeutic pressure. The dynamic changes of TCR from PBMC, when longitudinal blood samples are available, will be correlated to response to immune checkpoint blockade or chemotherapy and survival.

Details of time points and sampling are provided in the Schedules of Assessments (**Table 1**). An SOP detailing the tissue collection will be available to clinical team.

All proposed biomarker analyses are exploratory and dependent on the quality and availability of sufficient materials. The panel of biomarkers might be adjusted based on results from ongoing research related to anti-PD-1 / PD-L1 therapies and / or safety, therefore, each subject will also be asked whether any remaining tumor tissue and blood-derived samples can be stored at a central repository (until such time as these samples cannot support any further analysis) and can be used for future exploratory research on the drug and / or disease-related aspects. A subject's consent to the use of any remaining samples for such future exploratory research shall be optional and shall not affect the subject's participation in the current trial.

